6.3 Dose Modifications/Delays

As noted above, an individual patient who experiences DLT will have therapy held until resolution to grade 1 or less, and may then resume therapy at one dose level below their

previous level at the discretion of the investigator and treating physician. If the toxicity persists at >grade 1 for more than 4 weeks, the subject must be removed from the study.

In the Phase 2 study, all grade 3 (excluding asymptomatic laboratory abnormalities, or grade 3 nausea, vomiting or diarrhea readily controlled with appropriate supportive care) or grade 4 non-hematologic toxicities will result in at least temporary discontinuation from study drug. When the toxicity resolves to grade 1 or less, the treating physician and the Principal Investigator may make a decision about the appropriateness of continuing the patient on study. Toxicity grading is based on the CTEP Active Version of the NCI Common Terminology Criteria for Adverse Events (CTCAE) non-hematologic toxicities. Any non-hematologic toxicity (excluding asymptomatic laboratory abnormalities, or grade 3 nausea, vomiting or diarrhea readily controlled with appropriate supportive care) that persists at > grade 1 for more than four weeks will result in permanent discontinuation from the study.

Table 2: Dose-Modification

Dose-Modification		
	Dose Level	Reduce Dose To:
Starting Dose	150 mg	100 mg
	100 mg	50 mg
	50 mg	25 mg
	25 mg	12.5
	12.5	Hold

Subjects removed from the study for toxicity will be followed until initiation of next therapy or death.

6.3.1 Hematologic Toxicity

Hematologic toxicity will be graded according to IWCLL 2008 criteria¹⁹, as enumerated in the table below.

ANC / μl	Toxicity Grade	Decrease in Plts from Pre-Tx Value (Use this correction if starting plt count < 100,000)
>= 2,000	0	0-10%
>= 1,500 - 2000	1	11-24%
>= 1,000 – 1,500	2	25-49%

$\geq 500 - 1,000$	3	50-74%
< 500	4	$\geq 75\%$

Subjects will not be evaluable for hematologic toxicity, hematologic dose-limiting toxicity or holding of therapy based on low ANC if the starting ANC < 1000 or the starting ANC is greater than 1000 with the assistance of growth factors. The ANC may be supported by growth factors throughout study therapy for this group of patients. In particular, LGL patients with pre-existing neutropenia will not be evaluable for toxicity related to neutropenia and may continue study drug at their assigned dose regardless of neutrophil count.

Subjects with baseline platelets $< 20,000$ will not be evaluable for platelet toxicity. Subjects with baseline platelets $\geq 100,000$ will be evaluated per CTEP Active Version of the NCI Common Terminology Criteria for Adverse Events (CTCAE); i.e, do not use the correction in the table above for assessing platelet toxicity when baseline platelets $\geq 100,000$. When baseline and Cycle 1 Day 1 ANC and/or platelets differ, the lower of the two values should be used for assessing DLT, dose modifications and hematologic toxicity.

For subjects with initial ANC $\neq > 1000$, neutropenia grading will follow the table above and development of grade 4 neutropenia will result in temporary discontinuation of study drug. Consideration may be given to administration of folic acid, low-dose leucovorin or growth factors to these patients. Once recovery occurs subjects may be restarted at their previous dose. Those whose grade 4 ANC persists for at least 7 days despite these supportive care measures will be considered to have suffered dose limiting toxicity if this happens in the first cycle, only. If these subjects experiencing DLT are continued on study after resolution, they should undergo a one dose level reduction in dose. Although NOT considered a DLT in cycle 2 and beyond, if a subject experiences grade 4 ANC that persists for at least 7 days despite the supportive care measures listed above, the subject may undergo a one dose level reduction in dose at investigator discretion

Thrombocytopenia will be graded based on the table above, using adjusted parameters for all subjects with a starting platelet count $< 100,000$. For those subjects with a starting platelet count $\neq > 100,000$, development of thrombocytopenia will be graded based on CTEP Active Version of the NCI Common Terminology Criteria for Adverse Events (CTCAE). Any subject with a starting platelet count $< 20,000$ will not be evaluable for hematologic toxicity, hematologic dose-limiting toxicity or holding of therapy based on thrombocytopenia. For any subject with a starting platelet count $> 20,000$, development of a platelet count $< 20,000$ is considered grade 4 thrombocytopenia and will result in holding of study drug. Consideration may be given to administration of folic acid or low-dose leucovorin. Persistence of grade 4 thrombocytopenia for > 7 days despite these supportive care measures will be considered a DLT if this happens in the first cycle. If these subjects experiencing DLT are continued on study after resolution within one month, a dose reduction by one dose

level per the dose escalation table is required. If grade 4 thrombocytopenia persists for > 7 days in cycle 2 or beyond, consideration may be given to a one dose level reduction, at the discretion of the Principal Investigator and treating investigator.

6.3.2 Rash

For grade 3 or greater skin rash, study drug should be discontinued. If the rash resolves (back to grade 1 or less, within 4 weeks) with supportive care and is not IgE mediated or accompanied by other signs of allergic hypersensitivity, patients may resume study therapy at one lower dose level, or if already at the lowest dose level, may resume at that dose with addition of prophylactic antihistamine. Consideration may be given to use of a prophylactic antihistamine, particularly diphenhydramine, even in patients resuming at a reduced dose.

6.3.3 Anorexia/Vomiting:

For grades 1-4 anorexia/vomiting, study drug should be continued with initiation of antiemetic therapy. If drug needs to be held until patient can tolerate drug with supportive care, patient may resume at same dose level. If antiemetics do not bring relief, then the dose should be reduced one level. Patients with grade 3 or 4 anorexia/vomiting that do not respond to supportive care should be discontinued from study drug, but will remain on study for follow-up procedures until initiation of another therapy.

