5.3 Definition of Dose-Limiting Toxicity

Dose limiting toxicity (DLT) will be defined as any non-hematologic toxicity of grade 3 or greater severity (excluding asymptomatic grade 3 laboratory abnormalities that are not life-threatening and respond to treatment; grade 3 fatigue; grade 3 nausea, vomiting or diarrhea occurring without optimal prophylaxis). Infectious toxicities will only be considered dose-limiting if grade 4 or greater. Any grade 4 non-hematological toxicity, as well as any irreversible grade 2 cardiac, renal or neurologic toxicities, will be considered dose-limiting. Grading of non-hematologic toxicities will be according to CTEP Active Version of the NCI Common Terminology Criteria for Adverse Events (CTCAE). DLT refers to toxicities experienced during the first cycle of treatment only.

Hematologic toxicity will be graded according to the 2008 IWCLL criteria (see table in section 6.3.1 under dose modifications)¹⁹. Hematologic toxicity will only be considered dose-limiting as follows:

Grade 4 neutropenia persisting for at least 7 days after discontinuation of study drug in Cycle 1 only. Neutropenia will not be considered a DLT for subjects with T-LGL.

Grade 4 thrombocytopenia persisting for at least 7 days after discontinuation of drug in Cycle 1 only.

Abnormal hematologic values are not noted as inclusion or exclusion criteria. Subjects with starting ANC \leq 1000 (or greater than 1000 but requiring growth factor support) or starting platelet count \leq 20,000 will not be evaluable for hematologic toxicity or hematologic DLT, as per consensus recommendations for clinical trials in CLL and T-LGL. Determination of whether to hold pyrimethamine for hematologic toxicities will be determined in these patients on a case by case basis by the treating physician and the Principal Investigator. As in Section 5.4 following, growth factor support and/or platelet transfusion are allowed at the investigator's discretion.

Dose-limiting toxicities will be determined during the 1st 28-day cycle only. There are no DLT parameters post Cycle 1.

Management and dose modifications associated with the above adverse events are outlined in Section 6 (Expected Toxicities and Dosing Delays/Dose Modifications).

Dose escalation will proceed within each cohort according to the following scheme.

Number of Participants with DLT at a Given Dose Level	Escalation Decision Rule
0 out of 3	Enter 3 participants at the next dose level.

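### Section 6.3.3 says to continue drug, or restart at the same dose, for grade 4 anorexia/vomiting and grade 3 anorexia that section 6.3 says to hold and, after a DLT, restart one level lower

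*Combined protocol and SAP*

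**What the plan says.** Section 6.3.3 (Anorexia/Vomiting) has four steps:

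- First action: "For grades 1-4 anorexia/vomiting, study drug should be continued with initiation of antiemetic therapy".
- After a hold: "If drug needs to be held until patient can tolerate drug with supportive care, patient may resume at same dose level".
- Antiemetics fail: "If antiemetics do not bring relief, then the dose should be reduced one level".
- Severe events that do not respond: "Patients with grade 3 or 4 anorexia/vomiting that do not respond to supportive care should be discontinued from study drug".

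The first step covers grades 1 to 4 alike. The second has no grade limit and does not mention DLT.

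The parent section, 6.3, has two general rules. A patient with a DLT "will have therapy held until resolution to grade 1 or less, and may then resume therapy at one dose level below their" previous level. In Phase 2, grade 3 events outside a stated exemption "or grade 4 non-hematologic toxicities will result in at least temporary discontinuation from study drug". The exemption is narrow: "excluding asymptomatic laboratory abnormalities, or grade 3 nausea, vomiting or diarrhea readily controlled with appropriate supportive care".

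Section 5.3 decides what is a DLT, in cycle 1 only. Non-hematologic toxicity of grade 3 or higher counts, apart from listed exclusions. Those exclusions include grade 3 nausea, vomiting or diarrhea without optimal prophylaxis, but not anorexia. At grade 4 the rule is: "Any grade 4 non-hematological toxicity, as well as any irreversible grade 2 cardiac, renal or neurologic toxicities, will be considered dose-limiting".

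Section 5.1.2 is headed Subsequent Cycles but is worded for every toxicity that led to a hold. It requires recovery to grade 1 or less before drug is restarted.

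**The concern.** For one patient on one day, two current sections give opposite instructions. Grade 4 vomiting in cycle 1 is a DLT, so 6.3 stops drug while 6.3.3 continues it. If drug is stopped and antiemetics work, 6.3 brings the patient back one level lower while 6.3.3 permits the full dose. Nothing in the protocol ranks the two. The nursing education sheet refers staff to 6.3 for dose modification and to 6.3.3 for this toxicity in particular.

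What is at stake is patient safety at the new doses. Section 2.1 says anorexia and vomiting may occur at 50 mg daily; the added cohorts take 100 and 150 mg, two and three times that. The same section says vomiting usually clears promptly when the dose is lowered, which favors the step-down in 6.3. Drug given while antiemetics are tried is also slow to clear, with a half-life of about 96 hours (7.1.1). In addition, 5.2.1 tells patients to retake a dose vomited within an hour. Read with an instruction to continue, that could mean re-dosing a patient with grade 4 vomiting.

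**Working it through.** The plan gives no figure to reproduce. The check sets the rules side by side for each type of event.

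| Event | 5.3 and 6.3 | 6.3.3 | Result |
|---|---|---|---|
| Grade 4 anorexia or vomiting, cycle 1 | DLT: hold; any restart one level lower | Continue; same dose allowed after a hold | Conflict on hold and restart dose |
| Grade 3 anorexia, cycle 1 | DLT, since anorexia is not excluded: hold; any restart one level lower | As above | Conflict on hold and restart dose |
| Grade 3 vomiting despite optimal prophylaxis, cycle 1 | DLT: hold; any restart one level lower | As above; reduce or stop if supportive care fails | Restart dose conflicts if the event later responds; the hold conflicts while response is awaited |
| Grade 4 anorexia or vomiting, or grade 3 anorexia, Phase 2, not a DLT | Hold; no restart dose set | Continue | Conflict on the hold only |
| Grade 3 vomiting not readily controlled, Phase 2, not a DLT | Hold | Continue, then reduce or stop if supportive care fails | Partial: dosing while response is awaited |
| Grade 3 vomiting readily controlled, Phase 2, not a DLT | Exempt from the hold | Continue | None |
| Grade 3 vomiting without optimal prophylaxis, cycle 1 of Phase I | Not a DLT, so no hold | Continue | None |
| Any grade, Phase I after cycle 1 | No hold rule in 6.3 | Continue | None with 6.3 |

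**Restart condition.** Under 5.1.2 a held toxicity must be back to grade 1 or less. Under 6.3.3 the patient need only be able to tolerate drug with supportive care. These can differ: a patient may tolerate drug on antiemetics while still at grade 2.

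**Restart dose after a DLT**, from Table 2 in 6.3:

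- Level 5: 150 mg under 6.3.3 against 100 mg under 6.3; 150/100 = 1.5.
- Level 4: 100 mg against 50 mg; 100/50 = 2.

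**Related subsections.** In 6.3.1, neutropenia that did not become a DLT may restart at the previous dose, but neutropenia and platelet DLTs step down one level. In 6.3.2, rash of grade 3 or higher steps down one level unless the patient is already at the lowest. That rash rule is not written as a DLT rule, so the hematologic rules are the closer comparison. They separate DLT from non-DLT; 6.3.3 does not.

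**The case against.** The best reply is that the sections can be read together. 6.3.3 sits under 6.3, and its restart sentence is conditional on a hold. So 6.3 could decide when a hold is needed and supply the step-down after a DLT, and 5.1.2 could supply the grade threshold. On this view a same-dose restart after a DLT is inferred only from silence. That is a fair reading of the second sentence of 6.3.3, but it does not rescue the first, which orders continuation at grade 4 outright.

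Nor does it help to call 6.3.3 a specific exception to the general rule. The protocol does not say so. Section 6.3 already considered vomiting and exempted it only at grade 3 when readily controlled; that exemption would have no purpose if 6.3.3 governed all vomiting.

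There are real safeguards. 6.3.3 itself reduces the dose or stops drug when supportive care fails. Section 5.5 calls for removal of subjects with significant adverse events. The study calendar requires toxicity assessment before dosing on clinic days, and the nursing sheet tells staff to page the research nurse or site investigator with questions. These lower the risk. They leave the opposite first instruction in place, and they leave the restart dose unsettled when antiemetics work.

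A reader might infer more than the documents support:

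- *All grade 3 vomiting is in conflict.* It is not: 5.3 and 6.3 both exempt some of it. Section 5.4 requires no antiemetic premedication, so a first episode may well occur without prophylaxis and then not be a DLT.
- *6.3.3 keeps non-responders on drug.* It reduces or discontinues them.
- *The MTD decision is distorted.* Classification follows 5.3, whatever is done with the dose afterwards.
- *Phase I patients after cycle 1 are affected.* 6.3 has no hold rule for them.

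**Conclusion.** The contradiction stands, within limits. It is firm for grade 4 anorexia or vomiting and for grade 3 anorexia, whether as a cycle 1 DLT or in Phase 2. After any DLT that responds to supportive care, the restart dose also conflicts, by a factor of 1.5 at 150 mg and 2 at 100 mg. For grade 3 vomiting not readily controlled in Phase 2 the conflict is partial. In Phase 2 outside a DLT, 6.3 sets no restart dose, so only the hold is at issue, together with the grade 1 threshold in 5.1.2.

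This rests on reading the sections as written, with no rule of precedence. Restart after a DLT is discretionary under 6.3; what conflicts is the dose at which it may happen. The documents give no rate for these events, so the number of patients affected cannot be stated, and the conclusion does not depend on it. This is a safety instruction that should be corrected. It does not undermine the trial's design or its DLT data.

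**What to change.** Replace the first two sentences of 6.3.3 with:

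> For anorexia/vomiting that 6.3 does not require to be held, continue study drug with antiemetic therapy; if drug is held, resume at the same dose level once grade 1 or less (5.1.2). For any anorexia/vomiting that is a DLT, and in Phase 2 for grade 4 anorexia/vomiting, grade 3 anorexia, or grade 3 vomiting not readily controlled with supportive care, hold study drug until grade 1 or less per 6.3; after a DLT, resume only at one dose level lower.

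Keep the remaining sentences of 6.3.3 on dose reduction and discontinuation. This adds no mandatory hold in Phase I after cycle 1, where 6.3 has none.

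The cost is a wording amendment, which needs IRB approval under 13.1, and a few more short dose holds. The DLT definition, the text of 6.3, the sample size and the visit schedule do not change. The nursing sheet already points to both sections and needs no edit.

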5.1.2 Subsequent Cycles

All toxicities for which pyrimethamine was held must have resolved to grade 1 or less prior to re-initiation of study therapy. For a detailed discussion of the management of hematologic toxicity **please see section 6.3.1**

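### Section 6.3.3 continues study drug through grade 4 anorexia or vomiting and grade 3 anorexia, where Section 6.3 requires a hold

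*Combined protocol and SAP*

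**What the plan says.** Section 6.3.3 (Anorexia/Vomiting) sets its default action for all four grades: "For grades 1-4 anorexia/vomiting, study drug should be continued with initiation of antiemetic therapy". It then allows a hold if one is needed, with restart at the same dose once the drug is tolerated. It calls for a one-level reduction if antiemetics fail, and it stops drug for grade 3 or 4 events that do not respond to supportive care.

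Section 6.3 (Dose Modifications/Delays) has two hold rules.

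- DLT rule: "an individual patient who experiences DLT will have therapy held until resolution to grade 1 or less". The patient "may then resume therapy at one dose level below their" previous level, at the discretion of the investigator and treating physician.
- Phase 2 rule: grade 3 events "or grade 4 non-hematologic toxicities will result in at least temporary discontinuation from study drug". The grade 3 part has an exemption: "excluding asymptomatic laboratory abnormalities, or grade 3 nausea, vomiting or diarrhea readily controlled with appropriate supportive care".

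Section 5.3 defines DLTs, in Cycle 1 only. Grade 3 or higher non-hematologic toxicity counts, with exclusions that include "grade 3 fatigue; grade 3 nausea, vomiting or diarrhea occurring without optimal prophylaxis". At grade 4 there is no exclusion: "Any grade 4 non-hematological toxicity, as well as any irreversible grade 2 cardiac, renal or neurologic toxicities, will be considered dose-limiting".

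Section 5.1.2 adds a general restart condition: "All toxicities for which pyrimethamine was held must have resolved to grade 1 or less prior to re-initiation of study therapy".

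**The concern.** For some events the same patient on the same day is covered by one instruction to continue and another to hold. Anorexia and vomiting are listed effects of the drug (2.1 and 6.1.1). The completed cohorts reached 50 mg, and the added cohorts give 100 and 150 mg, so the reassuring safety statement in 1.1 does not cover the doses now planned.

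The difference can outlast the first day. Under 6.3.3 a Cycle 1 patient with grade 4 vomiting who improves on antiemetics need not miss a dose or step down. Under 6.3 that patient is held until grade 1 or less and, if restarted, resumes one level lower. Sites are likely to act on 6.3.3, because the nursing education sheet in the appendix points staff to it by number for this symptom.

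**Working it through.** No figure is at issue, so the check compares the rules event by event. Two readings of the text decide most rows. First, neither exclusion list (5.3 or the Phase 2 rule in 6.3) names anorexia; both name nausea, vomiting and diarrhea. Second, neither list exempts grade 4 anorexia or vomiting.

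| Event | 6.3.3 at onset | 6.3 with 5.3 | Result |
|---|---|---|---|
| Grade 4 anorexia or vomiting, Cycle 1 | Continue | DLT: hold | Conflict |
| Grade 4 anorexia or vomiting, Phase 2 | Continue | Hold | Conflict |
| Grade 3 anorexia, Cycle 1 | Continue | DLT: hold | Conflict |
| Grade 3 anorexia, Phase 2 | Continue | Hold | Conflict |
| Grade 3 vomiting despite optimal prophylaxis, Cycle 1 | Continue | DLT: hold | Conflict, less common |
| Grade 3 vomiting without optimal prophylaxis, Phase 1 Cycle 1 | Continue | Not a DLT: no hold required | None |
| Grade 3 vomiting, Phase 2 | Continue, treat | Hold only if not readily controlled | None at onset |
| Grades 1-2 | Continue | No hold required | None |
| Any grade, Phase 1 after Cycle 1 | Continue | No general hold rule | None |

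The fifth row is less common because 5.4 neither requires nor suggests antiemetic premedication, and 6.3.3 speaks of starting antiemetics. It mainly addresses patients not yet on prophylaxis, whose grade 3 vomiting 5.3 excludes.

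The Phase 2 grade 3 vomiting row is not a conflict at onset. Whether vomiting is readily controlled can be judged only after supportive care has been tried, and trying it is what 6.3.3 orders. If it fails, 6.3.3 reduces or stops the drug, which broadly agrees with 6.3.

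Precedence: no sentence says that 6.3.3 overrides 6.3. The neighbouring subsections are consistent with 6.3. Section 6.3.1 requires a one-level reduction after a neutropenia DLT, and 6.3.2 stops drug at grade 3 or higher rash and generally restarts it one level lower.

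**The case against.** The best defence is that a symptom-specific rule governs over a general one. Section 6 describes its guidance as recommendations, prefers symptomatic management and names antiemetics. Section 6.3.3 is also not an instruction to dose regardless: it permits a hold and stops grade 3-4 non-responders. Section 5.5 says subjects with significant adverse events should be removed, 5.7 requires immediate notice of life-threatening complications, and the study calendar has toxicity assessed before dosing on visit days.

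The safeguards are real and limit the risk. The precedence argument is plausible but unstated, and it would leave the grade 4 and DLT hold rules in 6.3 without effect for one of the drug's own listed toxicities. None of the safeguards says which rule applies to a patient who responds to antiemetics.

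A reader might also infer that the restart sentence in 6.3.3 is a second contradiction. The documents do not support that. The sentence is permissive and can be read as the non-DLT rule. Section 5.1.2 already covers every toxicity for which drug was held, 6.3 covers resumption after a DLT, and 6.3.1 has a comparable same-dose restart after recovery. A clarifying cross-reference is enough.

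**Conclusion.** The inconsistency is real and confined to grade 4 anorexia or vomiting, grade 3 anorexia, and Cycle 1 grade 3 vomiting despite optimal prophylaxis. It is worth correcting on safety grounds.

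The number of patients affected cannot be stated, because the documents give no rate for these events. Statistical impact is nil: 5.3 classifies an event as a DLT by type, grade and cycle, and for these events the action taken on dosing does not enter, so the escalation count is unchanged.

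Three broader readings should be resisted.

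- That all Phase 2 grade 3-4 events conflict. Grade 3 vomiting does not at onset, because of the supportive-care exemption.
- That 6.3.3 breaches a hold rule in Phase 1 after Cycle 1. Section 6.3 has no general hold rule there.
- That the half-life of about 96 hours gives a size of harm. Assuming first-order elimination, a 7-day hold would leave 2^(-168/96) = 0.30 of the drug level. But the comparison with continued dosing assumes that doses are absorbed in a vomiting patient and that no one uses the hold allowed in 6.3.3, and nothing in the documents links drug level to harm. It is an illustration only.

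The conclusion rests on the plain wording of the two exclusion lists and on the absence of any precedence statement.

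**What to change.** Amend 6.3.3 in two or three sentences:

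1. Limit continuation with antiemetics to events for which 6.3 requires no hold.
2. State that any anorexia or vomiting that is a DLT under 5.3 is held until grade 1 or less per 6.3. State that in Phase 2 the same applies to any grade 4 event, grade 3 anorexia, and grade 3 vomiting not readily controlled with supportive care.
3. State that same-dose restart applies only to non-DLT events, and that after a DLT 6.3 and Table 2 apply.

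Do not carry the readily-controlled test into Phase 1: there, grade 3 vomiting without optimal prophylaxis is not a DLT and 6.3 does not require a hold. Add no new hold rule for Phase 1 after Cycle 1. Leave the dose-reduction and non-responder sentences as they are.

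The cost is one amendment to one subsection, with no added patients or procedures. The downside is a few more dose holds.
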